7 EFFICACY ANALYSES

All efficacy analyses will be carried out using the Intent-to-treat Sample and Per-Protocol Sample.

7.1.1 Analysis of primary outcome variable

Efficacy analysis at the end of the study

The primary outcome measure for assessing effectiveness of ZNS (100 mg PO) either pre-op or post-op compared to the placebo group will be the proportion of subjects defined as PTS positive 30 days (+/-3 days) after surgery.

Audiogram will be performed to look for PTS. Patients for whom the difference at any frequency from 2-6 kHz in hearing thresholds (30 days (\pm -3 days) post-surgery - Baseline) is \geq 10 dB HL will be defined as PTS positive. Primary analysis and sensitivity analyses will be carried out on the primary endpoint.

Primary analysis

Frequency and relative frequency will be used to describe the distribution of the primary outcome measure in each study group. To assess efficacy, Fisher's exact test will be used to compare the proportion of subjects with PTS positive in ZNS group with the proportion of patients with PTS positive in the placebo group.

The confidence intervals will be calculated using method 10 described by Newcombe RG, 1998 and also described by Altman et al.

 Altman, Douglas, et al., eds. Statistics with confidence: confidence intervals and statistical guidelines. https://www.amazon.com/Statistics-Confidence-Intervals-Statistical-Guidelines/dp/0727913751

Let n_1 be the number of participants in placebo group, and r_1 the number of participants with PTS in the placebo group. $p_1=r_1/n_1$ be the proportion of PTS in the placebo group, and $q_1=r_2/n_2$ the proportion of participants that do not have PTS in placebo group.

 l_1 and u_1 are the lower and upper limits of the $100(1\text{-}\alpha)\%$ confidence interval for p_1

Using Wilson method we calculate:

$$A_1 = 2r_1 + z^2$$

$$B_1 = z\sqrt{z^2 + 4r_1q_1}$$

$$C_1 = 2(n_1 + z^2)$$

$$l_1 = \frac{(A_1 - B_1)}{c_1}$$
 $u_1 = \frac{(A_1 + B_1)}{c_1}$

 z_a = the 100(1 – α)th percentile of the standard Normal distribution.

Let n_2 be the number of participants in ZNS group, and r_2 the number of participants with PTS in the ZNS group. $p_2=r_2/n_2$ be the proportion of PTS in the ZNS group, and q_2 the proportion of participants that do not have PTS in ZNS group.

l₂ and u₂ are the lower and upper limits of the 100(1-α)% confidence interval for p₂

$$A_2 = 2r_2 + z^2$$

$$B_2 = z\sqrt{z^2 + 4r_2q_2}$$

$$C_2 = 2(n_2 + z^2)$$

$$l_2 = \frac{({\rm A}_2 - {\rm B}_2)}{c_2} \qquad \qquad u_2 = \frac{({\rm A}_2 + {\rm B}_2)}{c_2}$$

 z_a = the $100(1-\alpha)^{th}$ percentile of the standard Normal distribution.

The proportion difference between groups is: $\mathbf{D} = \mathbf{p_1} - \mathbf{p_2}$

The lower (l_D) and the upper limits (u_D)of 100 (1- α)% confidence interval for D will be calculated as:

$$l_D = D - \sqrt{(p_1 - l_1)^2 + (u_2 - p_2)^2}$$

$$u_D = D + \sqrt{(p_2 - l_2)^2 + (u_1 - p_1)^2}$$

A supportive logistic regression analysis will be done with covariates: age, pre-op hearing dichotomized to normal to minimal hearing loss and slight to mild loss, noise exposure history dichotomized to high risk and low risk, exposure categorized as low (8-hour equivalent A-weighted sound level in decibel (LAeq8hr) < 80 dBA), moderate (LAeq8hr > 80 dBA but < 90 dBA), or high (LAeq8hr > 90 dBA).

```
PROC LOGISTIC DATA=X;
CLASS GROUP;
   MODEL PTS = COVARIATE1 COVARIATE2.. ;/*Covariates are as mentioned above*/
RUN;
```

Sensitivity analysis of the primary endpoint

The potential impact of missing primary endpoint data will be explored in sensitivity analyses using multiple imputation. Two sensitivity analyses performed:

Sensitivity 1: MI analysis under the missing not at random assumption (MNAR) Sensitivity 2: Logistic regression tipping point analysis under the assumption of data missing at random.

Sensitivity 1

Proc MI procedure in SAS will be used to impute missing data for study treatment groups using the distribution implied by the non-missing patient data within the placebo group. The SAS code to impute data for Sensitivity analysis 1 under the MNAR assumption will be of the form:

```
PROC MI DATA=X SEED=<value> NIMPUTE=10 OUT=MI_OUT1 NOPRINT;
CLASS GROUP;
VAR AGE PTA LSurg......;
FCS LOGISTIC(PTS);
RUN;
```

Post imputation each of the imputed 10 datasets will be analyzed using the same approach as for the primary outcome measure. The estimates of the analysis of the 10 imputed datasets will be then combined following Rubin's rules using PROC MIANALYZE procedure in SAS which will be of the form:

```
PROC MIANALYZE PARMS=GMPARMS COVB=GMCOVB PARMINFO=GMPINFO WCOV BCOV

TCOV; / *dataset "gmparms" contains the estimates and associated standard errors
for the mean parameters from each of the M=10 imputed data sets.
dataset "gmcovb" contains the asymptotic covariance matrics
dataset "gmpinfo" contains parameter info*/

MODELEFFECTS INTERCEPT AGE PTA LSurg......;
RUN;
```

Sensitivity 2

Multiple imputation will be used to impute data in each of the study groups. A progressive penalty of $\delta_i = k_i \times \log{(OR)}$ will be added to imputed values in ZNS arm where (i) OR is the Odds ratio estimate for ZNS as compared to Placebo from the primary logistic regression analysis and (ii) $k_i = 1, 0.95, 0.90, \dots 0.05, 0, 1.05, 1.10,\dots$ thus k ranges from 1 (equivalent to MI approach based on MAR) to 0 (or higher), until the conclusion of the primary analysis is overturned (i.e., p<0.05 is lost at, this value of k_i being the 'tipping point'). Rubin's method will be used to combine the primary endpoint treatment effects across imputations for each value, k_i , of the penalty. Forest plots will be used to graphically display the penalty value that results in loss of statistical significance.

```
SAS code sample for Sensitivity analysis is provided below:

**Step 1: Generate 10 datasets by imputing the missing data**;

PROC MI DATA=X SEED=<value> NIMPUTE=10 OUT=MI_OUT1 NOPRINT;

CLASS GROUP;

VAR AGE PTA LSurg......;

FCS LOGISTIC (PTS);

RUN;

**Step 2: Generate 10 complete datasets from the 10 monotonized datasetsin Step 1 for missing values in the drug arm,
```

```
subtract DELTA derived above from their imputed data.**;
proc mi data=YYY NIMPUTE=1 SEED=<value> OUT=YYY shift;
by group;
class group;
var AGE PTA LSurg.....;
monotone method=logistic;
mnar adjust(PTS / shift=DELTA adjustobs=(group='1'));
**Step 3: Apply the primary MMRM to the 10 complete datasets in Step 2**;
proc genmod data=YYY shift descending;
by imputation;
class group;
model PTS = group AGE PTA LSurg......;
ods output GEEModPEst=gmparms;
**Step 4: Obtain the pooled inference from 10 sets of estimates from Step 3**;
PROC MIANALYZE PARMS=GMPARMS COVB=GMCOVB PARMINFO=GMPINFO WCOV BCOV
   TCOV:
   MODELEFFECTS group;
RUN:
```

7.1.2 Analysis for secondary outcome measures.

The focus of the study is to determine efficacy of ZNS for treatment of acute hearing loss based on the testing of hypothesis for primary outcome. In addition, we will also conduct analysis to evaluate other important audiologic measures. The secondary outcome measures are key audiological and clinical assessments of change in cochlear function and hearing loss: DPOAEs, ECochG, WIN testing. They will be measured as continuous level variables. We do not plan any adjustment of alpha error for multiple comparisons.

Analysis of variance (ANCOVA) will be used for comparison of outcome measures between each of the ZNS groups and placebo study group after controlling for baseline value and age, pre-op hearing dichotomized to normal to minimal hearing loss and slight to mild loss, noise exposure history dichotomized to high risk and low risk, exposure categorized as low (LAeq8hr < 80 dBA), moderate (LAeq8hr > 80 dBA but < 90 dBA), or high (LAeq8hr > 90 dBA).

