#### Primary analysis.

Frequency and relative frequency will be used to describe the distribution of the primary outcome measure in each study group. To assess efficacy, Fisher's exact test will be used to compare the proportion of subjects with PTS positive in ZNS group with the proportion of patients with PTS positive in the placebo group.

To provide an estimate of treatment effect a supportive logistic regression analysis will be done with covariates: age, pre-op hearing dichotomized to normal to minimal hearing loss and slight to mild loss, noise exposure history dichotomized to high risk and low risk, exposure categorized as low (8-hour equivalent A-weighted sound level in decibel (LAeq8hr) < 80 dBA), moderate (LAeq8hr > 80 dBA but < 90 dBA), or high (LAeq8hr > 90 dBA).

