2.4 Randomisation

Eligible subjects will be randomized in a balanced fashion into one of the 3 arms: ZNS 100 mg pre-op, Placebo, or ZNS 100 mg post-op. To balance noise-exposure history across study arms we will employ stratified randomization. The subjects will be stratified based on noise exposure survey responses (see table below), and will then be randomized to study groups. Randomization will be based on the randomization list generated by unblinded statistician using a computer algorithm written in SAS® using randomly selected blocks of sizes 3. Within each block of 3, there will be 1 subject assigned to each study group. The random assignment of subjects to the different study groups will be associated with consecutively assigned random numbers which will be unique for each study subject. The stratified kit list will be provided to Advanced Rx who will package and label the drug for shipment to the pharmacist. Each kit will contain two bottles and will be labeled with the same kit number. The bottle will not contain any information of the treatment allocation. One interim analysis is planned, once 33% (n=78) of the subjects have completed participation in the study.

Name	Description
1: High Noise	Screening: LENS-Q Adapted for Surgical Noise Study – 1A Or 2A Or 4A = a.Daily, Or b.Less than daily/more than weekly, Or c.Weekly, Or d.Less than weekly/more than monthly Or e.Monthly OR 1C Or 2C Or 3C >= 5 Years

Name	Description
2: Low Noise	Screening: LENS-Q Adapted for Surgical Noise Study – 1A AND 2A AND 4A = f.Less than monthly/more than yearly, g.Yearly, h.Less than yearly Or i.Never OR 1C AND 2C AND 3C < 5 Years

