2.7 Sample Size Determination for The Primary Efficacy Outcome Measure

The primary efficacy outcome will be the proportion of PTS positive subjects defined as the ratio of PTS-positive subjects to total number of subjects in each study arm/group. Using pilot data from a retrospective chart review of 75 similar patients undergoing \geq 1-hour drill noise exposure, we estimate the proportion of PTS positive subjects in the placebo group will be 50%. We hypothesize that the expected effect of ZNS either pre-op or post-op will be a 50% reduction of the proportion of subjects with PTS positive as compared to placebo group. This is the desired clinically significant effect for treating hearing loss for single dose of 100 mg ZNS.

The sample size for this study was calculated for the planned comparisons of each of the ZNS groups with the placebo group using a balanced design and a one-sided alpha level of 0.0125 Based on the data from our retrospective study, using Fisher's exact test we estimated that 78 subjects in the ZNS group and 78 subjects in the placebo group will be needed to provide us with 80.4 % power to detect a 50% reduction in the proportion of PTS positive subjects *(from 50% to*

^{**}Dispensed on the day of surgery with instruction to take first dose prior to surgery and second dose after surgery.

^{***} Plasma sample for PGx will be collected at baseline visit. Plasma sample for ZNS level and PGx, electrolyte panel, BUN, Cr, ALT, and AST will be collected 12 hours after first dose.

25% corresponding to an absolute proportion difference of 25%) at the 1-sided alpha level of 0.0125 for each ZNS-Placebo group comparison. A total of 234 subjects will be enrolled to be randomized in this study. All efforts will be made minimize and eliminate drop outs. Given the short term-follow-up of study subjects in a period where they are under medical care, few, if any, drop-outs or lost to follow-up are expected.

Sample size calculations were carried out using PROC POWER procedure in SAS 9.4.

3 Study Outcomes

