3.1 Primary estimand

The primary estimand for the study is: In adults with no more than a mild to moderate high-frequency hearing loss and who undergo drilling during skull-based surgery, what is the difference in the proportion of patients experiencing PTS in the contralateral ear (the proportion of PTS-positive subjects defined as the ratio of PTS-positive subjects (defined as all subjects who in audiogram are identified as having a PTS of > 10 dB HL increase at any frequency between 2-6 kHz post-surgery as compared to baseline audiogram) to total number of subjects in each study arm/group) between ZNS treatment compared to Placebo, 30 days (+/- 3 days) after randomization or death (whichever occurs first).

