3.2.2 Comparison of the proportion of PTS-positive patients between ZNS post-op and Placebo

$$H_0: p_{ZNS_{post-op}} - p_{Placebo} = 0$$
 $H_A: p_{ZNS_{post-op}} < p_{Placebo}$

We hypothesize that ZNS post-op will reduce the proportion of PTS-positive patients by an absolute difference of 25% as compared to placebo. Our one-sided hypothesis is supported by animal studies, and lack of any evidence of hearing loss as a side effect of ZNS in human studies. The statistical testing will be performed using Bonferroni method to control for type I error rate at one-sided alpha level of 0.0125.

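### The primary test is an unstratified Fisher test in a trial stratified by noise history; it is valid, but a less conservative, stratified test at the same nominal level would give about 4 more points of power, most of it from replacing Fisher itself.

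*SAP*

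**What the plan says.** - **Primary test.** SAP 7.1.1, and Protocol 12.2.1 in matching terms: Fisher's "exact test will be used to compare the proportion of subjects with PTS positive in ZNS group with the proportion of patients" on placebo. No strata or covariates enter it.
- **Level.** SAP 3.2.2 applies the "Bonferroni method to control for type I error rate at one-sided alpha level of 0.0125". SAP 2.7 sizes the trial "at the 1-sided alpha level of 0.0125 for each ZNS-Placebo group comparison".
- **Randomisation.** SAP 2.4: "To balance noise-exposure history across study arms we will employ stratified randomization". There are two strata, High and Low, from the noise questionnaire.
- **Estimand.** SAP 3.1 asks "what is the difference in the proportion of patients experiencing PTS in the contralateral ear". SAP 7.1.1 estimates this without adjustment, as a difference of two proportions with a Newcombe interval.
- **Adjusted analysis.** Protocol 12.2.1: "To provide an estimate of treatment effect a supportive logistic regression analysis will be done with covariates". The covariates are age, pre-op hearing in two classes, noise history, and surgical noise exposure in three classes. The model is logistic, so it yields an odds ratio.

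Neither document says why the stratification factor is left out of the deciding test, or how strongly noise history or baseline hearing predicts PTS.

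**The concern.** The sponsor treats noise history, age and baseline hearing as relevant to outcome. Noise history defines the strata, and all three are in the supportive logistic model and in every secondary ANCOVA. Only the deciding test ignores them.

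Two losses follow. First, Fisher's test does not spend its full nominal alpha at this sample size, and leaving out a prognostic stratum makes it more conservative still. Second, the only adjusted analysis reports an odds ratio, so no adjusted result exists on the scale of the estimand.

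At stake is power that needs no extra patients. The stated 80.4% leaves almost no margin.

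**Working it through.** **Inputs.** From SAP 2.7: 78 per arm, placebo rate 50%, ZNS rate 25% and one-sided alpha 0.0125, so z = 2.2414. The quoted bases are "we estimate the proportion of PTS positive subjects in the placebo group will be 50" per cent and "25% corresponding to an absolute proportion difference of 25" points. The prognostic strength of noise history and the share of High-noise subjects are not in the documents. They are assumed below and varied.

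**Step 1: reproduce the stated power.** The Walters arcsine approximation for Fisher's test is

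Power = Φ( √(2n) × [arcsin√(p1 − 1/(2n)) − arcsin√(p2 + 1/(2n))] − z ).

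With n = 78, the bracket is 0.2480 and √156 = 12.490. So 12.490 × 0.2480 − 2.2414 = 0.856, and Φ(0.856) = 80.4%. This matches the plan. Exact enumeration of all 2×2 tables gives 80.7%.

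**Step 2: unstratified alternatives on the same tables (exact enumeration).**

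| Test | Power | Maximum size |
|---|---|---|
| Fisher | 80.7% | 0.0100 |
| Boschloo | 84.6% | 0.0124 |
| Mid-p | 84.7% | 0.0125 |

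Fisher's size is 0.0077, 0.0083 and 0.0100 at common rates of 0.25, 0.375 and 0.50. The gain is 84.6 − 80.7 = 3.9 points for Boschloo and 84.7 − 80.7 = 4.0 for mid-p. Neither uses strata or covariates, so this part needs no assumption about prognosis.

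Mid-p does not guarantee its level. At 78 × 0.95 ≈ 74 per arm, the same enumeration gives it a maximum size of 0.0131. Boschloo's test holds the level by construction.

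**Step 3: what stratification adds.** This was simulated with marginal rates held at 50% and 25% and balanced allocation within strata. The Cochran-Mantel-Haenszel (CMH) statistic is Z = Σ(a_s − E_s) / √ΣV_s, summed over the two noise strata, where a_s is the ZNS event count in stratum s and E_s and V_s are its hypergeometric mean and variance.

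| High share | Stratum OR | Fisher | Mid-p | CMH | CMH − mid-p |
|---|---|---|---|---|---|
| 50% | 1 | 80.6% | 84.7% | 84.9% | 0.2 |
| 50% | 2 | 80.9% | 84.9% | 85.7% | 0.8 |
| 50% | 3 | 81.6% | 85.5% | 87.0% | 1.5 |
| 85% | 1 | 80.9% | 84.8% | 85.1% | 0.3 |
| 85% | 2 | 81.2% | 85.2% | 85.5% | 0.3 |
| 85% | 3 | 81.3% | 85.1% | 85.7% | 0.6 |

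At OR 4 with an even split, CMH reaches about 88% and adds about 2.4 to 2.7 points over mid-p, the top of the range.

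As a like-for-like check, an exact stratified conditional test gains only 0.1, 0.6 and 1.7 points over Fisher at OR 1, 2 and 3, because it keeps most of Fisher's conservatism.

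**Step 4: error rate.** At a null rate of 0.5, simulated CMH size is mostly about 0.012 to 0.013. A check with 400,000 trials per setting gave 0.0116 to 0.0134 (Monte Carlo SE about 0.0002). Asymptotic CMH can therefore slightly exceed 0.0125.

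**Step 5: continuous baseline covariate.** A score test with noise stratum and one continuous baseline covariate gains about 6 to 8 points over Fisher at an assumed log-odds of 0.5 per SD, and about 10 at 1.0 per SD. Both strengths are assumptions.

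All figures are per comparison and ignore the futility look and dropout.

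**The case against.** The strongest reply is that nothing is wrong with the plan. Fisher's test guarantees its level, the stated power is met, and an unadjusted comparison in a randomised trial is valid. This stands, and it is why the point concerns efficiency only.

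Four stronger readings are tempting, and the documents do not support them.

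- **That ignoring the strata costs the whole gain.** Boschloo's test ignores them too and recovers 3.9 points. The noise stratum contributes roughly 0 to 2. It may be lopsided: five years or more in one's occupation is enough for High noise (Protocol Appendix F, item 1C), whether or not that work was noisy.
- **That the power is free at the same error rate.** Only the nominal level is the same. Fisher's real size is at most 0.0100, and the alternatives use alpha that it leaves unspent.
- **That the estimand goes unestimated.** The Newcombe interval in SAP 7.1.1 is for the difference in proportions. Only an adjusted estimate on that scale is missing.
- **That the supportive logistic model could simply be promoted.** Its surgical noise covariate is recorded during the operation (Protocol 5.4), after randomisation. It also cuts baseline hearing into two classes, and the sample code in SAP 7.1.1 has no treatment term in its model statement.

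It is also fair to object that Fisher's test is built into other parts of the plan. SAP 5.2 pools z-values derived from Fisher p-values across imputations, and SAP 9 derives the futility z the same way. The change therefore reaches beyond one sentence.

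**Conclusion.** The point holds as a recommended improvement. At 78 per arm, 50% against 25% and nominal one-sided 0.0125, Fisher's test gives 80.7% power with true size of about 0.008 to 0.010. Replacing it with a less conservative unstratified test gives about 84.6 to 84.7%, a gain of about 4 points that rests only on the plan's own inputs.

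Stratifying by noise history adds roughly 0 to 2 points for an assumed stratum odds ratio of 1 to 4, and less if most subjects are High noise. A continuous baseline-hearing covariate may add more, but that depends on a prognostic strength the documents do not give. The case for using the strata rests as much on matching the analysis to the randomisation, and on an adjusted estimate on the estimand's scale, as on power.

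**What to change.** Before any unblinding, amend Protocol 12.2.1 and SAP 7.1.1:

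1. Make the primary test and the risk difference stratified by the randomised noise stratum. Preferably adjust also for age and continuous baseline 2-6 kHz threshold, and report a standardised risk difference. Leave out surgical noise exposure, which is measured after randomisation.
2. Take the p-value from a method that holds one-sided 0.0125, such as re-randomisation within strata, rather than from asymptotic CMH.
3. Keep Fisher's test and the Newcombe interval as a sensitivity analysis.
4. Make the matching changes to the imputation pooling (SAP 5.2 and the missing-data text in Protocol 12.2) and to the interim z-value (SAP 9, Protocol 12.4). State how the p-value is obtained across imputations, and recheck the futility bound and its quoted overall power for the new statistic.

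The sample size can stay. The cost is conforming edits in those sections, programming and validation of the new test, an analysis slightly harder to describe, and the use of alpha that Fisher leaves unspent. No patients, visits or data are added.

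### SAP 7.1.1 gives the wrong formula for q1 and an inconsistent z and confidence level, so the interval for the primary PTS difference is wrong if programmed as printed

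*SAP*

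**What the plan says.** SAP 7.1.1 (Primary analysis) compares each ZNS arm with placebo by Fisher's exact test and then specifies an interval for the difference: "The confidence intervals will be calculated using method 10 described by" a cited source. The formulas follow step by step: Wilson limits for each arm, then the limits for D = p1 − p2, with placebo as arm 1 and ZNS as arm 2.

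For placebo, the text reads "q_1=r_2/n_2$ the proportion of participants that do not have PTS in placebo group". A few lines later, for ZNS, it reads "p_2=r_2/n_2$ be the proportion of PTS in the ZNS group". The ZNS counterpart q2 is described in words only.

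On the level, the single-arm statement is "l₂ and u₂ are the lower and upper limits of the 100(1-α)% confidence interval for p₂", and the limits for D carry the same 100(1−α)% label. In both arms z is "the 100(1 – α)th percentile of the standard Normal distribution". No numerical α is attached to the interval. The nearest value is in SAP 3.2.2, where testing is meant to "control for type I error rate at one-sided alpha level of 0.0125" (also SAP 2.7), but that value belongs to the tests and is not linked to the interval. Protocol 12.2.1 gives no interval formula that would settle the matter.

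**The concern.** There are two separate faults.

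- **q1.** The symbol is given the wrong arm and the wrong outcome. As printed, q1 equals p2, so the placebo limits depend on ZNS data, and the shared placebo arm would get different Wilson limits in the two comparisons.
- **z and level.** A two-sided interval with z at the 100(1−α)th percentile has nominal level 100(1−2α)%, not 100(1−α)%. With no α given, a reader cannot tell whether the reported interval is meant as 95%, 97.5% or 98.75%.

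This is the only interval specified for the primary difference, which is the quantity named in the estimand (SAP 3.1), and it is set out in a form a programmer would code directly. At stake is the reported precision of the main result and whether the interval agrees with the test beside it.

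**Working it through.** **Inputs.** 78 per arm, placebo 50%, ZNS 25%, one-sided α = 0.0125 (SAP 2.7 and 3.2.2); interval formulas from SAP 7.1.1. The SAP sets no α for the interval, so α = 0.0125 is an assumption here, with other values shown in step 5.

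**1. The plan's own figure.** The stated power is 80.4%. Exact enumeration of one-sided Fisher at 0.0125 gives 80.7%, and an arcsine approximation with continuity correction gives 80.4%. The design inputs therefore reproduce.

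**2. When the printed q1 is harmless.** Printed q1 = r2/n2 = p2; the words require 1 − p1. They are equal only if p1 + p2 = 1. The planning rates sum to 0.50 + 0.25 = 0.75. With a sum below 1 the printed interval is too narrow; with a sum above 1 it is too wide.

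**3. Worked example, 39/78 v 20/78.** z = 2.2414, z² = 5.024, D = 0.5000 − 0.2564 = 0.2436.

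- A1 = 2(39) + 5.024 = 83.024; C1 = 2(78 + 5.024) = 166.048.
- Printed: q1 = 20/78, so 4·r1·q1 = 40 and B1 = 2.2414·√45.024 = 15.040. Placebo limits 0.409 to 0.591.
- Corrected: q1 = 39/78, so 4·r1·q1 = 78 and B1 = 2.2414·√83.024 = 20.423. Placebo limits 0.377 to 0.623.
- ZNS limits, both versions: 0.163 to 0.380.
- Printed interval for D: 0.2436 − √(0.0906² + 0.1232²) = 0.091, to 0.2436 + √(0.0937² + 0.0906²) = 0.374.
- Corrected interval for D, with 0.1230 replacing 0.0906: 0.070 to 0.398.
- Widths 28.3 v 32.9 points, ratio 0.86, so the printed interval is 14% too narrow.

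**4. Size of the q1 slip alone (z = 2.2414).** Coverage by full enumeration of two binomials, 78 per arm:

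| Placebo / ZNS | Printed | Corrected | Mean width ratio |
|---|---|---|---|
| 50% / 25% | 94.3% | 97.5% | 0.857 |
| 40% / 20% | 92.5% | 97.4% | 0.794 |
| 30% / 15% | 91.0% | 97.6% | 0.748 |
| 70% / 60% | 99.2% | 97.5% | 1.201 |

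Agreement with the one-sided Fisher test at 0.0125, limits in points:

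| Data | Fisher p | Printed | Corrected |
|---|---|---|---|
| 39/78 v 26/78 | 0.0255, not significant | 0.4 to 31.4 | −1.0 to 32.9 |
| 55/78 v 40/78 | 0.0106, significant | −0.8 to 37.5 | 1.7 to 35.2 |

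At 50%/25%, the interval excludes zero without Fisher significance in 9.4% of trials as printed and 4.4% as corrected. The printed limits can also leave the unit interval: for 70/78 v 40/78 the upper placebo limit is 1.038, which a Wilson limit cannot be.

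**5. The z and level fault, at 50%/25%.**

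| α assumed | SAP label | Coverage, SAP z, correct q1 | Coverage, SAP z, printed q1 |
|---|---|---|---|
| 0.0125 | 98.75% | 97.5% | 94.3% |
| 0.025 | 97.5% | 94.9% | 90.2% |
| 0.05 | 95% | 90.0% | 83.8% |

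If α = 0.0125 was intended, z = 2.2414 is the right multiplier for a two-sided 97.5% interval and only the 98.75% label is wrong. A true 98.75% interval needs z = 2.4977; for 39/78 v 20/78 it runs from 0.050 to 0.414.

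**The case against.** The strongest reply is that this is a typing error that competent programming would correct. The words beside the formula define q1 properly, q2 has no formula so the programmer must already form a complement for arm 2, the method is named, the combination formulas for D are right, and SAP 11.2 requires independent double programming. That makes literal coding less likely, and the harm is conditional on it. It does not remove the problem: both programmers work from specifications defined in the SAP, so if both follow the printed formula their outputs will match.

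Second, on the only α the SAP gives for these comparisons, the z fault moves no limit. That is correct; on that reading this part is a labelling error. The 90.2% and 83.8% figures depend on values of α that the SAP does not assign to this interval and should carry little weight.

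Third, the two directions of conflict with the test are not equally relevant. At 50%/25% the printed interval almost never includes zero when Fisher is significant (probability about 1e-8); the 55/78 v 40/78 example needs a placebo rate near 70%. In the other direction the slip adds about 5 points (9.4% against 4.4%), because a correctly coded Newcombe interval also disagrees with the conservative Fisher test at times. These points limit the size of the concern; the specification remains wrong as written.

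**Conclusion.** The concern holds. The q1 formula contradicts its own description, the percentile and the label do not match, and the interval has no stated α. If coded as printed with α = 0.0125, an interval with z suited to 97.5% covers 94.3% at the planning rates, falls to 91.0% at 30%/15%, and over-covers (99.2%) at 70%/60%. These figures assume 78 analysed per arm and independent binomial outcomes. The consequence is confined to the reported effect interval; efficacy is decided by Fisher's test, and that decision, its type I error, the power and the sample size do not change. It should be corrected before the analysis is programmed.

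**What to change.** In SAP 7.1.1:

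- Set q1 = 1 − r1/n1 and q2 = 1 − r2/n2.
- Define z as the 100(1−α/2)th percentile, and state the level once: a two-sided 97.5% Newcombe interval for each ZNS–placebo comparison (α = 0.025 for the interval, z = 2.2414), which corresponds to the one-sided 0.0125 test. If the sponsor prefers to keep α = 0.0125 throughout, keeping the present percentile and relabelling the limits 100(1−2α)% gives the same interval.
- Add a short note that this interval can still occasionally exclude zero when Fisher is not significant (about 4.4% of trials at the planning rates), and that Fisher's test decides.

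The cost is a few lines of SAP text. Data collection, design, primary test and sample size stay as they are. If α = 0.0125 was always intended, z stays at 2.2414 and only q1 and the label change in the calculation and its reporting.

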#### 3.0 ELIGIBILITY CRITERIA

#### 3.1 Inclusion Criteria

- 1. Patients who are scheduled to undergo a skull-based surgery that requires at least 45 minutes of surgical-drilling.
- 2. At least 18 years of age.
- 3. Air conduction thresholds in the non-operated ears are to be no worse than 25 dB HL for pure tone average 0.5, 1, and 2 kHz with no individual threshold greater than 30 dB HL, and no worse than 45 dB HL at 4 kHz at screening.
- 4. Observed air-bone gap  $\leq$  10 dB HL at 0.5, 1, 2, and 4 kHz, with normal tympanometry.
- 5. Ability to understand and willingness to sign an IRB approved written informed consent document.

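### The two-class pre-op hearing covariate has no defined measure or cut-off and its labels stop at mild loss, while the estimand includes moderate high-frequency loss; a continuous 2-6 kHz baseline would serve better

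*SAP*

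**What the plan says.** The primary analysis is an unadjusted Fisher's exact test. Beside it, SAP 7.1.1 states: "A supportive logistic regression analysis will be done with covariates: age", followed by "pre-op hearing dichotomized to normal to minimal hearing loss and slight to mild loss", noise-exposure history and surgical noise level. Protocol 12.2.1 has the same model and says that it is there to estimate the treatment effect. SAP 7.1.2 and Protocol 12.2.2 carry the same two classes into the ANCOVAs for DPOAE, ECochG and WIN, which compare the arms "after controlling for baseline value and age, pre-op hearing dichotomized to normal to minimal hearing loss and slight to mild loss".

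Three other places bear on this covariate:

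- **Estimand (SAP 3.1).** The population is described thus: "In adults with no more than a mild to moderate high-frequency hearing loss".
- **Eligibility (Protocol 3.1).** The non-operated ear must be "no worse than 25 dB HL for pure tone average 0.5, 1, and 2 kHz", with no single threshold above 30 dB HL, and "no worse than 45 dB HL at 4 kHz at screening". No limit is set at 3 or 6 kHz.
- **Code (SAP 5.2 and 7.1.1).** The imputation statements read "VAR AGE PTA LSurg". The Sensitivity 2 model regresses PTS on group, AGE, PTA and LSurg, with only the group variable in its CLASS statement. PTA is not defined in the analysis sections or in the SAP's abbreviation list.

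**The concern.** The upper class ends at mild loss, but the SAP's own population goes further. A programmer cannot derive the variable from the plan. The measure and cut-off would have to be chosen later, outside the plan, and the choice could decide which subjects enter the adjusted models.

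The logistic odds ratio also has a second use. The Sensitivity 2 tipping-point penalty is k × log(OR), with OR taken from the logistic regression. An odds ratio from a logistic model depends on which covariates are in it and in what form. The definition of the hearing covariate therefore carries through to a sensitivity analysis of the primary endpoint.

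**Working it through.** **1. The plan's own figure.** Inputs from SAP 2.7: 78 per arm, 50% v 25%, one-sided alpha 0.0125, Fisher's exact test, stated power 80.4%. The Walters arcsine approximation with continuity correction is

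power = Φ{2[asin√(0.5 − 1/156) − asin√(0.25 + 1/156)]·√(78/2) − z(0.9875)} = 80.41%.

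Exact enumeration gives 80.7%. The stated figure reproduces. The test contains no covariate, so nothing below changes it.

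**2. The possible gradings, set against the documents.**

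- *High-frequency thresholds.* SAP 3.1 admits moderate high-frequency loss, and neither class label covers it. The missing-data text (SAP 5.2) deals with missing PTS and gives no rule for a subject without a hearing class. PROC LOGISTIC by default omits records with a missing covariate.
- *Average of 0.5, 1 and 2 kHz.* Every eligible subject is at 25 dB HL or better, so everyone can be classed. PTS, however, is scored on "Patients for whom the difference at any frequency from 2-6 kHz in hearing thresholds". Of 2, 3, 4 and 6 kHz (the frequencies listed in Protocol 4.0 for the NIOSH definition), only 2 kHz enters the covariate.
- *Average of 0.5, 1, 2 and 4 kHz.* The ceiling is (3 × 25 + 45)/4 = 30 dB HL. The documents give no scale that says which class this is.

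**3. Information kept by a two-class split.** For a normal covariate (assumed) with a fraction q in the lower class and cut-point c, the share of linear information retained is φ(c)²/[q(1 − q)]:

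- q = 0.5: 64% kept
- q = 0.8: 49% kept
- q = 0.9: 34% kept

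The loss is therefore 36% to 66% over this range.

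**4. Effect on power of the supportive model.** Simulation of 78 v 78 subjects with marginal rates of 50% and 25%, a normal covariate, a Wald test at one-sided 0.0125 and 3,000 runs per row. Monte Carlo error is about √(0.866 × 0.134/3000) = 0.6 points per figure. The log odds ratios per SD and the 10% share without a class are assumptions; the documents give neither. There are two sets of runs (A and B), so compare within rows.

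| Set, log OR per SD | No covariate | 80:20 split | Median split | Continuous | Median split, worst 10% dropped |
|---|---|---|---|---|---|
| A, 0.5 | – | – | 84.6% | 85.3% | 80.8% |
| A, 0.8 | – | – | 88.0% | 89.2% | 83.9% |
| A, 1.1 | – | – | 89.0% | 91.5% | 86.1% |
| B, 0.5 | 85.6% | 86.0% | 86.4% | 86.6% | 81.9% |
| B, 1.0 | 84.9% | 87.4% | 88.4% | 89.8% | 85.1% |

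Differences in points, in row order:

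- Continuous minus median split: 0.7, 1.2, 2.5, 0.2, 1.4.
- Continuous minus 80:20 split (set B only): 0.6, 2.4.
- Continuous minus median split with 10% dropped: 4.5, 5.3, 5.4, 4.7, 4.7.
- Median split with everyone minus median split with 10% dropped: 3.8, 4.1, 2.9, 4.5, 3.3.

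The third line combines two effects. The fourth isolates the dropping of subjects, which accounts for most of it. The figures near 85% without a covariate exceed 80.4% because the Wald test is less conservative than Fisher's test (pooled normal approximation: 84.6%). That gap is not a gain from adjustment.

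**The case against.** A reader might infer that moderate-loss subjects certainly have no class and will be excluded. The documents do not support this. They never say that the classes are graded on high frequencies, they give no dB boundary between mild and moderate, and they do not say that an unclassed subject is dropped. The only pure tone average in the eligibility criteria is 0.5, 1 and 2 kHz, the code variable is called PTA, and dichotomising suggests that everyone is placed in one of two groups. So exclusion is conditional on the grading.

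A reader might also infer that this logistic model is the plan's only covariate-adjusted estimate. It is not. Sensitivity 2 fits and pools an adjusted group effect with PTA outside the CLASS statement, which points to a continuous variable. This is not conclusive, because a 0/1 variable would also run that way. The plan thus appears to treat baseline hearing in two ways for the same endpoint, which argues for aligning them.

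Two further points stand. The ANCOVAs already adjust for the outcome's own baseline, and their outcomes are not 2-6 kHz thresholds, so the case for change is weaker there. And the logistic model is supportive, with no alpha or power assigned to it. Splitting a covariate in two there is a modest inefficiency, and an open-ended upper class would by itself cure any exclusion.

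What this does not answer is that the covariate is undefined and that its labels are narrower than the estimand's population.

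**Conclusion.** The point holds as a mismatch and a missing definition, with a modest loss of efficiency. The labels stop short of the population in SAP 3.1, and no measure, frequency or cut-off is stated. One natural grading could lose eligible subjects; another neglects most of the endpoint's frequency range.

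The effect is confined to the supportive logistic model, the tipping-point penalty that borrows its odds ratio, and to a lesser degree the ANCOVAs. The primary test, its sample size and its 80.4% power do not change. In the supportive model, the continuous covariate is worth about 0 to 2.5 power points if everyone is classed and about 4.5 to 5.5 points if 10% would otherwise be dropped. These sizes rest on an assumed normal covariate, log odds ratios per SD of 0.5 to 1.1, and the assumed 10%. The ANCOVAs were not simulated. The change is worth making because it is better defined, keeps every eligible subject and needs no new data.

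**What to change.** **Logistic regression (SAP 7.1.1, Protocol 12.2.1).** Replace the two classes with the non-operated ear's baseline mean threshold over 2-6 kHz, in dB HL, as a continuous covariate, and list the frequencies averaged.

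**Sensitivity 2 (same sections).** Use the same variable in place of the undefined PTA, so that the model and the odds ratio behind its penalty rest on one definition of baseline hearing.

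**ANCOVAs (SAP 7.1.2, Protocol 12.2.2).** Use the same continuous variable. If classes are kept, state the measure, frequencies and dB cut-off, and make the upper class open-ended so that every eligible subject has a class.

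**Cost.** Wording in the SAP and protocol, to be settled before unblinding. Protocol 5.1 already requires a baseline audiogram from 250 Hz to 16 kHz and records an absent threshold as the equipment limit plus 10 dB, so every tested subject will have a value.
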